9.1 Data Management

The final transfer to the sponsor will include all tables, listings, graphs supported by this analysis plan in PDF format. All analysis datasets and documentation (analysis dataset programming specs) that support statistical analyses included in this analysis plan will be made available upon request from the sponsor. All data and documents requested will be transferred to the sponsor by using a secure transfer method.

9.2 Analysis Populations

Modified Intent-to-Treat: All safety and effectiveness measures will be analyzed on a modified intent-to-treat basis. Modified means that only patients who complete the TKR

procedure will be analyzed according to the treatment in which they were randomized, regardless of whether or not they completed all protocol requirements. As such, all randomized and TKR surgical patients will be included in the Modified Intent-To-Treat (MITT) Population. The exception will be if a patient withdraws consent to participation and requests in writing that all data previously collected be removed from the study.

Subjects who are randomized but do not have a TKR procedure will be noted in subject-specific listings but will not be included in tabulated results. This will include subjects who have not received their surgery at the cut-off time designated by the study team, so that close-out procedures and statistical compilation of data can be done.

9.3 Data from Multiple Sites

The VERITAS study is a multi-center clinical trial within sites in the United States. Approximately six orthopedic surgical practice groups will be selected to enroll patients in the trial. Sites will be identified and approached based on estimated surgery volume, and the availability of staff resources to support successful participation. Site selection will be limited geographically to a 50-mile radius around the Durham-Chapel Hill Comprehensive Joint Replacement (CJR) bundle region to minimize the variation of in-hospital costs. Site start-up may be staged to allow for controlled run-in of the first patients at each site.

The site where a subject was randomized is included as part of the randomization strata. Exploratory analyses will include assessing the influence of site on treatment effects for both the primary and secondary endpoints. This will be done by adding a fixed-effect main site effect and interaction term between randomization strata (site) and treatment in a generalized linear model used to analyze the primary and secondary endpoints. This is described in more detail in Section 9.12 of this document.

9.4 Accounting for Missing Data

Missing data will not be imputed. We will analyze only available information.

9.6 Baseline Data Collection Form

9.6.1 Demographics

Baseline demographic and patient characteristic data (including age, sex, height, weight, race, ethnicity, marital status, work status and insurance) will be tabulated overall and compared by treatment group. Race will also be categorized as White, Black, Other or Multiple races for statistical comparative purposes. Body mass index (BMI) will be computed using height and weight [BMI = weight (kg) / height² (m²)].

9.6.2 Medical History and Physical Assessments

Medical history and comorbidities will be summarized overall and compared by treatment group using frequency counts and percentages. Continuous assessments including height, weight, 10-meter gait speed (if collected), heart rate and blood pressure and will be summarized overall and by treatment group as n, mean, standard deviation (SD), median, 25th and 75th percentiles, min and max with comparisons between groups using the appropriate method based on the variable distribution.

9.6.3 Baseline Patient Survey

Self-reported history and activity level will be summarized overall and by treatment group and will be compared between treatment groups using appropriate statistical methods.

Additional survey data collected will include personal recovery goals (goal and current score), the Satisfaction with Physical Function Survey, the PROMIS Global Health Survey, and the KOOS Knee Survey Questionnaire. Responses will be tabulated overall and by treatment group for each individual question response; however, no statistical comparisons will be done.

The overall scores generated from each of the Satisfaction, PROMIS and KOOS surveys (overall and subdomain scores) at baseline will be compared between treatment groups using the appropriate statistical procedure to evaluate baseline balance.

9.7 Discharge Data Collection Form

Summary of patient disposition will include time from consent until time of surgery (TKR) and time from surgery until discharge, both measured in days. Other data that will be summarized overall and by treatment group include discharge status, procedure completion status, pain score, 10-meter gait speed, and falls during the hospital stay. Discharge destination will also be summarized as home vs. other for statistical comparative purposes.

9.8 Follow-up Data Collection Forms

9.8.1 6-Week Data Collection

Standard clinical follow-up for TKR patients occurs approximately 6 weeks after surgery. At this routine visit, patients will be administered standard clinical assessments for gait speed and range of motion (ROM) in the operated knee. Six-week data captured will

include the time from surgery until the date of the 6-week visit in days. Ten-meter gait speed and range of motion (ROM) upper and lower scores will be tabulated overall and by treatment group. Comparisons between treatment groups will be based on an analysis as described Sections 9.11 and 9.12.

9.8.2 6-Week Patient Survey

The DCRI call center captures patient-reported outcome measured 6 weeks after surgery, including fallen since hospital discharge (yes/no), pain score, physical activity (frequency and duration of exercise) and return to work (yes/no, and if yes, same or modified schedule). These 6-week variables will be summarized overall and by treatment group.

The KOOS Knee Survey Questionnaire will also be administered at 6-weeks. Responses will be tabulated overall and by treatment group for each question response as well as for the total score; however, no statistical comparisons will be done on the individual responses. The KOOS junior can be used at the 6-week visit. The overall KOOS score will be evaluated for both superiority and non-inferiority at 6-weeks, while the KOOS subdomain scores will only be compared for superiority as part of the exploratory analyses.

9.8.3 3-Month Patient Survey

At this visit, patients will be again be contacted by the DCRI call center to capture patient-reported outcomes, including fallen since last interview (yes/no), pain score, total re-hospitalizations since discharge, physical activity (frequency and duration of exercise) and return to work (yes/no, and if yes, same or modified schedule).

Additional survey data collected will include the Satisfaction with Physical Function Survey, the PROMIS Global Health Survey, the PROMIS Global Mental Survey, and the KOOS Knee Survey Questionnaire. Responses will be tabulated overall and by treatment group for each question response; however, no statistical comparisons will be done for the individual responses. The overall KOOS score and individual subscale scores will be compared. The KOOS junior cannot be used at the 3 month time point for efficacy analysis but can be used to evaluate change from 6 weeks to 3 months.

The Net Promoter Score (how likely it is that you would recommend virtual physical therapy) will also be summarized within the subjects randomized to virtual rehab on a scale from 0 (not likely) to 10 (likely).

Additional variables collected at both 6- and 12-weeks but compared only at 12-weeks include healthcare encounters, adherence to prescribed PT regimen ((# days per week, adherence [5 categories], and reasons not done as prescribed) and progress toward personal recovery goal will be summarized using both categorical and continuous variables. Each type (PT visit, PT call/email, doctor visit, doctor call/email, urgent care visit, ER visit and hospitalization) will be summarized as incidence rate (Yes/No) and the number of encounters.

9.9 Power and Sample Size Calculations

The primary aim of this study is to assess the difference in outpatient post-surgical costs between the control and intervention groups at 12-weeks post-operative. The exact post-procedure cost estimates under study are unknown; however, we can estimate that an effect size of approximately 0.33 can be detected with 150 subjects per group with at least 80% power. The effect size is the ratio of the mean difference over the standard deviation (SD) assumed for each population. Lower variability would enable detection of a smaller cost difference, or the detection of a larger difference with fewer patients. The sample size estimates were made assuming a two-sample t-test with equal variance and a significance level of 0.05. Thus, with 300 subjects we can detect an effect size of 0.33 which represents a whole scenario of cost differences that can be detected with at least 80% power that is dependent on the variability of the costs under study. The below table illustrates some example cost differences that could be detected based on the assumed SD of the costs.

Standard Deviation (SD)	Mean Cost Difference (\$)	Standard Deviation (SD)	Mean Cost Difference (\$)
100	32.50	800	259.60
200	64.90	900	292.10
300	97.40	1000	324.50
400	129.80	1100	357.00
500	162.30	1200	389.50
600	194.70	1300	421.90
700	227.20	1400	454.40
750	243.40	1500	486.80

9.10 Primary Effectiveness Analysis

The total health service use costs at 12-weeks post-operative will be compared between patients who receive tele-rehab-supported PT (virtual group) versus traditional home and/or clinic-based PT (control group) for TKR. The primary cost comparisons will be done using an analysis of variance (ANOVA) method for continuous variables if (1) the dependent variable is normally distributed or (2) can be normalized using a transformation such as the logarithm or square root. The underlying assumptions of the statistical test procedure will be verified through non-normality tests and plots. If there is strong evidence that the assumptions are not met or cannot be met with an appropriate distribution, the nonparametric Wilcoxon Rank sum test will be used.

The total health service use costs at 12-weeks post-operative will be the primary effectiveness endpoint for this study. This will be calculated using a fee-for-service model and assigned costs. Tele-health for rehabilitation services was not a reimbursable service at the start of the trial, and thus a total intervention cost, including direct and indirect time with physical therapy and any in-person visits, is assigned using the following units and costs:

Healthcare Encounter	Unit	Cost
Intervention	Total (all interactions)	\$600
Home health PT	<5 visits (cost per visit) ≥5 visits (single cost per 60-day episode)	\$133 \$2,325
Outpatient clinic PT	Single visit	\$90
PT call/email	Single interaction	n/a
Doctor's office	Single visit	\$150
Doctor's office call/email	Single interaction	n/a
Urgent care or ER visit	Single visit	\$250
Re-hospitalization	Full length of one inpatient stay	\$7,825
Inpatient rehab facility	Full length of stay	\$10,720
Skilled nursing facility	Full length of stay	\$6,510

Intervention Group Patients: Total costs will be calculated as the assigned cost of the intervention plus assigned costs for any reported doctor's office visits, urgent care or ER visits, re-hospitalizations, and inpatient rehabilitation or skilled nursing facility stays in the 12 weeks following discharge from the surgical hospital stay. The formula is as follows:

Cost = intervention cost + (# of doctors office visits * \$150) + (# of ER/UC visits * \$250) + (# of re-hospitalizations * \$7,825) + (# of skilled nursing facility stays * \$6,510) + (# of inpatient rehabilitation facility stays * \$10,720)

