1.3. Rationale for VERITAS Randomized Controlled Trial

The use of digital technology where the patient and therapist can interact both in real-time and asynchronously (e.g., patient completes recommended activities and therapist reviews performance at different times) can alleviate scheduling issues for both the therapists and patients, allowing therapists to potentially manage more patients (higher case load) and patients to follow recommendations and complete activities when most convenient. Having the PT program entirely available to the patient via technology may be cost efficient for both the patient and health system as more therapy sessions could be completed by the patient on their own schedule, without co-pays, and requiring less real-time PT supervision over time. The primary aim of this project is to determine if a technology-supported home-based PT rehabilitation program is a cost-saving approach and at least clinically equivalent to traditional PT.

2. Study Aims

The goals of this research study are the following:

1. To compare the effects of tele-rehab-supported PT versus traditional home and/or clinic-based PT for TKR on 90-day health service use costs.
Hypothesis (Superiority): Patients who receive tele-rehab-supported PT will have lower total 90-day episode of care costs compared with patients in the traditional PT group.
2. To compare tele-rehab-supported PT and traditional PT on patient-centered outcomes
 - a. Effectiveness hypothesis (Non-Inferiority): The tele-rehab intervention will be non-inferior to traditional PT at 6 weeks (differences between groups <5% for clinical and patient-reported outcomes) and 12 weeks (difference <5% patient-reported outcomes).
 - b. Safety hypothesis (Non-Inferiority): The tele-rehab intervention will be non-inferior to traditional PT at 12 weeks (pain, self-reported number of re-hospitalizations and number of reported falls).
3. To explore whether individual patient characteristics are associated with differential improvement from 6 to 12 weeks assessed by patient-reported outcomes.

3. Study Design

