4.2.5 Patient Diary

Sites will be provided copies of a diary form to be given to each patient after randomization, as a method to support recall of healthcare interactions during the 6- and 12-week follow-up interviews. Patients will be instructed to use the diary to collect any interactions with the healthcare system that occur after they are discharged from the hospital following their surgery. Encounters of interest will include in-person PT visits, doctor visits, phone calls or emails to a PT or doctor, visits to an urgent care center or emergency room, and hospitalizations. Patients will also be instructed to rate weekly (on Sunday) their level of achievement of their self-selected

personal recovery goal. Data recorded on the diary will be collected from the patient verbally by the DCRI Call Center during the planned follow-up interviews.

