- Healthcare encounters since hospital discharge, and weekly status of personal recovery goal (patient diary entries)

4.5 12 Weeks Post-Op

At approximately 12 weeks after surgery, the patient will be contacted again by the DCRI Call Center to collect the following data via telephone interview. The interview is expected to last approximately 20 minutes:

- Surveys regarding health (KOOS, PROMIS, Satisfaction with Physical Function)
- Adherence to prescribed PT regimen
- Physical activity
- Falls since last interview
- Healthcare encounters since last interview, and weekly status of personal recovery goal (patient diary entries)
- Thoughts about the tele-rehab platform (intervention patients only)

Also at 12 weeks after surgery, select sites may be asked to provide a summary of enrolled patients' outpatient clinic encounters (phone, email, in person) with orthopedic staff and physical therapists. This may be used to validate patient-reported encounters from the diary. Collection of the information, if requested, may be facilitated using the medical record release form signed by the patient at the time of enrollment.

5. Statistical Methods

The goal of this study is to assess the cost of the episode of care for total knee replacement, and whether the use of a tele-rehab platform is successful in mitigating some of those costs. The episode for analysis will be from surgery through 3 months post-discharge, in alignment with the new Comprehensive Care for Joint Replacement (CJR) bundled payment model being piloted by the Centers for Medicare and Medicaid Services (CMS). This will be a time-driven activity-based cost (TDABC) analysis. DCRI will be responsible for regular reporting of enrollment statistics, data quality, and data query status to the sponsor.

In addition to assessing the primary objective of cost, the study also will assess standard clinical measures of recovery (range of motion, gait speed) and qualitative measures of patient perceptions regarding their health and functional status (patient surveys) using both standardized and non-standardized tools. These assessments are intended to demonstrate the non-inferiority hypothesis that patients receiving PT via the tele-rehab platform did not have worse outcomes than patients receiving traditional in-person PT.

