5 OVERVIEW

As background for the statistical methods presented below, this section provides an overview of the study objectives and design. It must be understood that this overview is a summary only, and that the protocol is the definitive reference for all matters discussed in what follows.

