6.2 Study Objectives

6.2.1 Primary Objective:

The primary objective is to compare the effects of tele-rehab-supported PT versus traditional home and/or clinic-based PT for TKR on health service use costs at 12-weeks postoperative.

Hypothesis (Superiority Test): Patients who receive tele-rehab-supported PT will have lower total episode of care costs compared with patients in the traditional PT group at 12-weeks.

6.2.2 Secondary Objective:

The secondary objectives are to compare tele-rehab-supported PT and traditional PT on patient-centered outcomes as follows:

- a. Effectiveness hypothesis (Non-Inferiority Test): The tele-rehab intervention will be non-inferior to traditional PT at 6 weeks (differences between groups <5% for clinical and patient-reported outcomes) and 12 weeks (difference <5% patient-reported outcomes).
- b. Safety hypothesis (Non-Inferiority Test): The tele-rehab intervention will be non-inferior to traditional PT at 12 weeks (pain, falls, and self-reported number of re-hospitalizations).

6.2.3 Exploratory Objectives:

The final objectives (exploratory analyses) are to determine if superiority between PT methods exist for the endpoints primarily tested for non-inferiority, determine whether individual patient characteristics are associated with differential improvement from 6 to 12 weeks assessed by patient-reported outcomes, and to determine the cost for the VERA system such that the cost between the control group and intervention groups is cost-neutral, assuming that the intervention group is determined to cost less.

7 Study Design

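### The SAP replaces the protocol's time-driven episode cost with fee-for-service prices for post-discharge encounters, does not declare the change, and keeps the episode-cost hypothesis

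*SAP*

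**What the plan says.** **Protocol.** Section 5 states the costing method: "This will be a time-driven activity-based cost (TDABC) analysis". It also states the window: "The episode for analysis will be from surgery through 3 months post-discharge". Aim 1 in section 2 hypothesises that tele-rehab patients "will have lower total 90-day episode of care costs compared with patients in the traditional PT group". Section 5.1 gives a narrower scope, describing the primary aim as the difference in outpatient costs after surgery. Section 4.2.5 has patients record in the diary "any interactions with the healthcare system that occur after they are discharged from the hospital following their surgery".

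**SAP.** Section 9.10 says of the primary endpoint: "This will be calculated using a fee-for-service model and assigned costs". Its table prices clinic PT, home health PT, doctor visits, urgent care or ER visits, re-hospitalizations and facility stays, and marks PT and doctor calls and emails n/a. For the intervention, "a total intervention cost, including direct and indirect time with physical therapy and any in-person visits, is assigned": a flat $600 for all interactions. The intervention formula adds priced encounters in the 12 weeks after the surgical discharge, and section 7.2.1 gives the diary as the source. Section 6.2.1 nevertheless hypothesises that tele-rehab patients "will have lower total episode of care costs compared with patients in the traditional PT group at 12-weeks".

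SAP section 10, the place for changes from the protocol, lists only the non-inferiority margins. SAP section 1 lists only a correction of one unit price. SAP section 5 says of the study objectives and design that "the protocol is the definitive reference for all matters discussed in what follows".

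**The concern.** The two documents define the primary endpoint with different instruments. TDABC builds cost from the time that staff spend. The SAP multiplies reported encounters by fixed prices and gives every intervention patient the same PT cost, so therapist effort in that arm cannot move the endpoint. The components differ as well: the protocol's episode begins at surgery, while the SAP's sum begins at discharge.

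What is at stake is the primary conclusion. The SAP's test can show that priced service use after discharge is lower. Under the hypothesis in SAP 6.2.1, that would be reported as a lower total cost of the episode. The intervention begins before surgery with prehab, so an effect on the index stay is possible, and the cost endpoint could not register it in either direction.

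**Working it through.** **Step 1. The plan's own power figure.** Inputs from Protocol 5.1: 150 per arm, effect size 0.3255, two-sample t-test with equal variance, alpha 0.05 (two-sided in SAP 9.10). Noncentrality = 0.3255 × √(150/2) = 2.819 on 298 degrees of freedom. Power = 0.8023, as tabulated. The effect size detectable with 80% power is 0.32455, and 0.32455 × $1,500 = $486.82 against the tabulated $486.80. The arithmetic is sound and is not in dispute. It does not say which cost the SD belongs to, and both documents state that the cost estimates are unknown.

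**Step 2. The definitions side by side.**

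| | Protocol | SAP |
|---|---|---|
| Method | TDABC (section 5) | Assigned fee-for-service prices, flat $600 for the intervention (9.10) |
| Start | Surgery (section 5) | Discharge (9.10 formula; diary in 7.2.1) |
| End | 3 months after discharge (section 5); 90-day episode, origin not stated (Aim 1) | 12 weeks after surgery (6.2.1, 7.2.1, opening of 9.10); 12 weeks after discharge (9.10 formula) |
| Scope label | Total episode cost (Aim 1); outpatient post-surgical cost (5.1) | Total episode cost (6.2.1); total health service use cost (7.2.1, 9.10); outpatient post-surgical cost (9.9) |
| Follow-up calls | Timed from surgery (4.4, 4.5) and from discharge (3.6.3) | Timed from discharge (8.2) |

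**Step 3. Days not observed.** Let L be the index stay in days, assumed to be 1 to 3 because the documents give no figure. Take 3 months as 90 days and 12 weeks as 84 days.

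- Both windows from the same origin: 90 − 84 = 6 days (6.7% of 90).
- 90 days from discharge, observed to 84 days after surgery: 90 − (84 − L) = 7, 8 or 9 days (up to 10.0%).
- 90 days from surgery, observed to 84 days after discharge: 90 − (84 + L) = 5, 4 or 3 days (down to 3.3%).

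The range is 3 to 9 days.

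**Step 4. What restoring the index stay could do to power (illustration).** Assume that the stay adds an independent cost with SD equal to k times a post-discharge SD of $1,500. The total SD is $1,500 × √(1 + k²).

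- k = 0.5: SD $1,677; detectable difference 0.32455 × 1,677 = $544; power for $486.80 falls to 70.7%.
- k = 1: SD $2,121; detectable difference $688; power 50.8%.

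No document gives k. The point is only that the tabulated differences cannot be carried from one definition to the other.

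**Step 5. Pre-operative PT.** Intervention patients receive prehab (Protocol 3.4.1), and the $600 is described as covering all interactions. Control patients receive prehab as their site recommends (Protocol 3.4.2), but the diary starts after discharge. If control prehab costs c per patient on average and is not counted, the control mean is too low by c. The break-even VERA price in SAP 9.12 is the control mean minus the intervention arm's other costs, so it is too low by the same c. The error works against the intervention.

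**The case against.** The strongest reply is that the SAP is open about its method. Section 9.10 gives the model, the prices and the intervention formula, and its test refers to health service use cost. The episode wording survives only in the 6.2.1 hypothesis, where it is qualified as at 12 weeks. The protocol also conflicts with itself: its sample-size section describes outpatient post-surgical cost, which is close to what the SAP computes. That stands, and it means the fault is not simply a SAP departing from a coherent protocol. It does not remove the problem, because the hypothesis and the formula still disagree and section 10 is silent.

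The index stay is not wholly ignored. SAP 9.7 summarises surgery-to-discharge days, and calls and emails are counted and compared separately (7.3, 9.8.3). Protocol 3.2 restricts sites geographically to limit variation in in-hospital costs. That may reduce differences between sites, but it does not rule out a difference between arms.

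Three stronger readings are tempting and are not supported:

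- That the protocol fixes a window of 90 days from surgery. No section says so, and Aim 1 gives no origin.
- That leaving out control prehab tilts the result toward the intervention. The direction is the opposite, and the omission is itself an inference. The SAP does not say that the $600 includes prehab, and the control formula was not in the text available for this review.
- That the omitted control prehab can be priced and shown to exceed the detectable difference. No document gives a number of visits, and the answer would depend on which SD row is chosen.

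**Conclusion.** The concern holds. The costing method, the components and the window of the primary endpoint all changed between protocol and SAP. The change is not declared, and one SAP hypothesis still claims the wider quantity. This rests on the visible text: the price table, the intervention formula, the diary as data source and SAP section 10.

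The main defect is the mismatch between claim and measure, which has no single dollar size because the documents give neither an SD nor a mean for the protocol's episode cost. The timing gap of 3 to 9 days is secondary and depends on the assumed 1 to 3 day stay. The difference in handling pre-operative PT is a probable limitation that works against the intervention. A reader might infer that the SAP's cost comparison is invalid. The documents do not support that: it is a usable comparison of a narrower quantity, under too wide a label.

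**What to change.** 1. In SAP 6.2.1, 7.2.1 and 9.10, name the endpoint and hypothesis *post-discharge health-service cost at assigned fee-for-service prices through 12 weeks*. State one time origin and remove the episode-of-care claim.
2. In SAP section 10, declare the move from TDABC to fee-for-service pricing, the exclusion of the index stay, and the change of window. Describe the protocol's window in its own two forms (section 5 and Aim 1), not as 90 days from surgery. Reconcile Aim 1, Protocol section 5, Protocol 5.1 and SAP 9.9 on scope.
3. Show surgery-to-discharge days by arm, already derived under SAP 9.7, beside the primary result.
4. State as a limitation that control pre-operative PT appears to fall outside the diary window while the $600 covers all interactions. If so, control cost is understated, which works against the intervention and lowers the 9.12 break-even price.

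The cost is document wording and one existing summary moved next to the primary table. No new data collection is needed. The downside is a narrower headline claim.
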